3.4. SEATTLE/PUGET SOUND—CHILDREN'S HOSPITAL & REGIONAL MEDICAL CENTER

The Seattle center is located in Seattle at the Children's Hospital & Regional Medical Center (CHRMC). For both the prevalence and incidence components of the study children with diabetes who reside in the five counties that comprise the Puget Sound Region of Washington (King, Kitsap, Pierce, Snohomish, Thurston) will be asked to participate.

Prevalent cases will be identified using a combination of clinical and non-clinical and administrative data sources including the following: pediatric and adult endocrinology practices in the Puget Sound region, the two major pediatric hospitals serving Puget Sound region, other hospitals with a history of admitting youth with diabetes, primary care clinics, data from the Community Diabetes Initiative (CDI) diabetes registry, the Group Health diabetes registry, the Washington State Comprehensive Hospital Abstract Reporting System (CHARS), and administrative data from four health plans (Medicaid, Group Health, and the two largest private insurers). For the incidence component of SEARCH, the Washington center will apply the same case identification strategies to identification of incident cases.

The Seattle center will use the U.S. census as the source of denominator estimates.

In 2000, approximately 1 million children and youth less than 20 years of age resided in the five counties of Puget Sound. This is the most populous and ethnically diverse region in the state, with approximately 6% African Americans, 5% Hispanics, 9% Asians/Pacific Islanders, and 1% Native Americans.

3.5. SOUTH CAROLINA

The South Carolina center is located in Columbia, South Carolina at the University of South Carolina (USC). For the prevalence component of the study, children with diabetes who reside in a four-county area (Richland, Lexington, Orangeburg and Calhoun) will be asked to participate. The majority of these cases were included in the Richland/Lexington County Child and Adolescent Diabetes Registry (RLDR). For the incidence component of the study, case ascertainment will be expanded to all 46 counties in South Carolina.

In 1999, the Richland/Lexington County Child and Adolescent Diabetes Registry (RLDR) was started by [name], a SEARCH PI, and colleagues to document the population prevalence of physician-diagnosed diabetes among individuals aged 0-18 years in a two-county region of South Carolina. Information for the registry comes from the following: the four hospitals in Richland and Lexington counties, the single pediatric endocrinologist serving the two counties, the two adult endocrinology practices, the USC pediatric outpatient clinic and family medicine clinics, the five largest private pediatric clinics, the three largest Family Medicine practices and camp lists provided by Camp Adam Fisher for children with diabetes. For the prevalence component of SEARCH, the South Carolina center will apply the same case identification methods used in the previous two-county registry. For the incidence component of SEARCH, the South Carolina will expand its case identification to all of South Carolina applying the same case identification strategies but with reliance on rapid case reporting by pediatric endocrinologists.

The South Carolina center will use the U.S. census as the source of denominator estimates.

In 2000, approximately 1.1 million children and youth less than 20 years of age resided in South Carolina, including about 39% of non-white racial/ethnic background. South Carolina ranks 14th nationwide on the poverty scale and 23% of children under age 19 live in poverty. 19.9% of the non-white, and 13.9 % of the white population are uninsured. 32% of South Carolina children do not graduate from high school. Over 30.5% of South Carolina children live in rural counties and 75% of the state's 46 counties are designated by the US Public Health Service as "medically under-served".

3.6. SOUTHERN CALIFORNIA KAISER PERMANENTE

This Kaiser Permanente Southern California (KPSC) center is located in Pasadena, California at the Department of Research and Evaluation. For both the prevalence and incidence components of the study, children with diabetes who are members of KPSC other than members in San Diego (SD) will be identified and invited to participate.

Kaiser Permanente is a group model HMO that delivers comprehensive medical care on a prepaid basis to 3 million resident of southern California. The Department of Research and Evaluation is the internal research arm of KPSC that is committed to the conduct of research in the public domain. Starting in 1995, [name], a SEARCH PI, initiated the KPSC diabetes case identification database as a resource for research and quality assessment and improvement. The database builds on work done in other Kaiser Permanente regions, using computer record linkage to identify possible cases of diabetes. For the prevalence component of SEARCH, the KPSC center will use the information in the existing computer database. For the incidence component of SEARCH, cases will be identified using a rapid reporting system of clinics and physicians supplemented with computer-stored data on prescriptions and laboratory testing.

The Kaiser Permanente Southern California center will use its administrative membership database as the source of denominator information. Estimates of the number of children in each ethnic group will be made based on block-level geocoding of address information to the 2000 U.S. census.

In 2000, approximately 700,000 children and youth less than 20 years of age were members of the Kaiser Permanente Southern California other than in San Diego, including about 29% of Hispanic, 10% African American, and 11% of Asian/Pacific Islander ethnic/racial origin. The KPSC membership less than 20 years of age includes about 45,000 children who are members of the Health Plan via Medicaid or other programs designed to provide low-income families with access to insurance.

Table 3 - 1: Description of Base Population and Summary of Source of Estimates Cases for Prevalence Component

	Base Population	Source of Cases	2001 Estimated, Denominator / Cases
Cincinnati (Children's Hospital)	Cincinnati and 8 surrounding urban counties (Hamilton, Butler, Warren, Clermont OH; Boone, Kenton, Campbell KY; Dearborn IN).	Existing pediatric diabetes database based on clinical visits to Children's Hospital	550,430 / 1,036
Colorado (University of Colorado Health Sciences Center)	Thirteen counties in Colorado; All interested Native American reservations in Arizona and New Mexico	Diabetes registry to be established	808,503 / 1,430
Hawaii (Pacific Health Research Institute)	Members of the Hawaii Medical Service Association, Kaiser Foundation Health Plan - Hawaii, and the Hawaii State Department of Human Services, Med-QUEST Division, in Oahu county.	Existing diabetes database based on record linkage	240,260 / 535
Seattle (Children's Hospital)	King, Pierce, Snohomish, Kitsap, Thurston counties	Diabetes registry to be established	982,920 / 1,735
South Carolina (University of South Carolina)	Richard, Lexington, Orangeburg, Calhoun counties	Existing network of sources including pediatric and adult endocrinologists, hospitals incl. Outpatient clinics, federally funded primary health care clinic	179,238 / 361
Southern California (Kaiser Permanente Southern California)	Members of the Kaiser Permanente Medical Care Program in Southern California except San Diego	Existing pediatric diabetes case identification database based on record linkage	700,450 / 1,281
All Sites			3,461,801 / 6,378

Table 3 - 2: Description of Base Population and Summary of Source of Estimated Cases for Incidence Component

	Base Population	Source of Cases	2001 Estimated, Denominator / Annual Cases
Cincinnati (Children's Hospital)	Cincinnati and 8 surrounding urban counties (Hamilton, Butler, Warren, Clermont OH; Boone, Kenton, Campbell KY; Dearborn IN).	New cases seen at Children's; referral to study by reporting network of pediatric endocrinologists	550,430 / 89
Colorado (University of Colorado Health Sciences Center)	All counties in Colorado; All interested Native American reservations in Arizona and New Mexico	Referral to study by reporting network of clinics, pediatric endocrinologists, and diabetes educators; updated diabetes registry to be established	1,420,839 / 217
Hawaii (Pacific Health Research Institute)	Members of the Hawaii Medical Service Association, Kaiser Foundation Health Plan - Hawaii, and the Hawaii State Department of Human Services, Med-QUEST Division, in all counties in Hawaii.	Referral to study by reporting network of clinics and pediatric endocrinologists; updated record linkage database	300,327 / 42
Seattle (Children's Hospital)	King, Pierce, Snohomish, Kitsap, Thurston counties	Referral to study by reporting network of clinics, pediatric and adult endocrinologists, hospitals supplemented with record linkage	982,920 / 151
South Carolina (University of South Carolina)	All counties in South Carolina	Referral to study by reporting network of clinics, pediatric and adult endocrinologists, hospitals supplemented with record linkage	1,118,022 / 183
Southern California (Kaiser Permanente Southern California)	Members of the Kaiser Permanente Medical Care Program Health Plan in Southern California except San Diego	Referral to study by KPSC reporting network of pediatric endocrinologists; quarterly updated record linkage database	700,450 / 103
All Sites			5,072,988 / 785

SEARCH Protocol – Section 4
Case Ascertainment
Table of Contents

4. METHODS: GENERAL OVERVIEW.....	2
4.1. GOAL.....	2
4.2. DENOMINATOR ESTIMATION	2
4.2.1. Prevalence Component	4
4.2.1.1. Eligibility Criteria.....	4
4.2.1.2. Case Finding Approaches	5
4.2.1.3. Case Validation.....	6
4.2.1.4. Estimated Number of Prevalent Cases.....	7
4.2.2. Incidence Component of SEARCH	7
4.2.2.1. Eligibility Criteria.....	7
4.2.2.2. Case Validation.....	8
4.2.2.3. Estimated Number of Incident Cases.....	9
4.2.3. Identification and Elimination of Possible Duplicate Cases	9
4.2.4. Gestational Diabetes	11
4.3. ASSESSMENT OF THE COMPLETENESS OF CASE ASCERTAINMENT.....	11
4.3.1. Capture-Recapture	11
4.3.2. Intensive Case-Finding	12
4.3.3. Use of Death Certificates	12
4.4. ASSESSMENT OF POSSIBLE BIAS DUE TO INCOMPLETE/MISSING INFORMATION ON VALIDATED CASES	13

4. Methods: General Overview

4.1. GOAL

The goal of case ascertainment is to identify and validate all unique, eligible cases of diabetes in youth less than 20 years residing in the SEARCH prevalence area in 2001 and all unique, eligible, newly diagnosed cases of diabetes in youth less than 20 years residing in the SEARCH incidence area in 2002-2004. This will allow SEARCH to estimate the population prevalence and incidence of childhood type 1, type 2, and other types (or hybrids) of diabetes.

This section provides a general overview of the methods that will be used to accomplish the goal (Methods: General Overview), as well as more detailed site-specific information (Methods: Site-Specific Case Ascertainment Methods)

To identify cases for SEARCH it is necessary to review protected health information. Access to such information is subject to federal regulation, state laws and institutional policies. SEARCH is aware of these regulations and addresses them in Section 11.

4.2. DENOMINATOR ESTIMATION

Overview

To estimate incidence and prevalence accurately, it is necessary to align the numerator and the denominator. That is, the cases of diabetes that are counted in the numerator for prevalence and incidence must derive from the same population that is defined as the denominator. To estimate incidence and prevalence accurately, it is also necessary to have accurate information on the denominator of children 0-19 years of age in which diabetes cases exist (for prevalence) or occur (for incidence). Every effort will be made in SEARCH to assure that numerator and denominator are aligned by applying the same criteria for inclusion in the denominator to eligibility for the study and to include case-finding data sources that would identify cases that would arise from the denominator.

The four geographically based SEARCH centers (Cincinnati, Colorado, Seattle, South Carolina) will use the US Census non-institutionalized non-military resident population in the area from which cases are drawn as the total denominator for estimation of prevalence and incidence. For the prevalence component of the study, 2000 US Census data will be used. For the incidence component of SEARCH, the geographically based centers will use projections of population changes based on the 2000 Census. A resident is defined by the Census as a person with a permanent address within the defined

geographic area at any time in the index year, who is not noted to be living elsewhere or only temporarily residing at the eligible address.

The membership-based centers (Hawaii and Southern California) will use administrative data on membership 0-19 years in the participating health plans as the total denominator for estimation of both incidence and prevalence. For both the prevalence and incidence components of the study, the number of health plan members on July 1 in the given year will be used.

Special populations

College students are counted in the Census in their residence location as of April 1. This will usually be the college/town where they attend school. An attempt will be made to identify diabetes cases in age-eligible college students resident in geographic areas of SEARCH case ascertainment so that numerator and denominator will be aligned. Youth who are attending college while still members of the participating health plans cannot be identified as attending college using administrative data. Thus, they will be included in the denominator for the member-based centers. Prevalent cases in college students are likely to be known to SEARCH and incident cases can be identified through member databases. Thus, numerator and denominator remain aligned. The handling of college students is also consistent between the geographically based and membership-based sites by including these youth in both the numerator and denominator.

Military personnel are counted in the Census at the base/community where they are assigned. Initial total population estimates include these persons. However, as the Census results are further refined, the military personnel are identified separately. No attempt will be made to identify diabetes cases in active-duty military personnel. Thus, final numerator and denominator estimates will exclude active-duty military service members.

Military dependents are counted in the Census at their usual residence, whether on or off base. Thus, they will be counted in the non-military denominator. Medical care for dependents will differ between base locations and access to care systems (military or civilian) will determine the ability to identify cases. Every attempt will be made to identify such cases in a consistent way across centers to align numerator and denominator similarly across sites. Center specific documents define how each center will identify cases in the military dependent population.

Institutionalized persons living in prisons, chronic care hospitals, and other institutions are removed from the counts of the civilian, non-institutionalized denominator, and will not be eligible as cases to align numerator and denominator.

Age, Gender, and Race/Ethnicity: Prevalence

For the geographically based centers (Cincinnati, Colorado, Seattle, South Carolina), Census data by age, gender and race/ethnicity will be used to estimate the number of persons in the denominator by age, gender and race/ethnicity. Year 2000 Census data will be used to calculate age, gender, and race/ethnicity specific denominators.

For the membership-based Hawaii center, it will be assumed that membership in the participating health plans is representative of the population of Hawaii with regard to race/ethnicity. The Census proportions of the Hawaii population aged 0-19 years by race/ethnicity will be applied to the age and sex-specific membership denominators.

For the membership-based Southern California center, direct counts of members 0-19 years by age and gender will be obtained from membership records. Data on race/ethnicity will be obtained by linking address information to block-level data from the Census using a process called geocoding.

For all centers, race/ethnicity data will be collapsed into groups (Non-Hispanic white, Hispanic American, African American, Asian, Pacific Islander, Native American, Other and Unknown) using rules and conventions developed by the Census.

Age, Gender, and Race/Ethnicity: Incidence

For years 2002 and beyond of the incidence study, the geographically-based sites (Cincinnati, Colorado, Seattle, South Carolina) will use projections of population changes that are based on the 2000 Census. The methods for making these projections will vary by location, but will be standardized as much as possible across sites using demographically acceptable methods. Population projections may not be available by age, gender, and race/ethnicity at the level of detail needed. Projected denominators, therefore, will be estimated using 2000 Census proportions by gender and race/ethnicity within age-specific groups, at least through 2005.

For the membership-based centers (Hawaii and Southern California), membership counts by age and gender will be updated annually. For each of these sites, Census projections of race/ethnicity will be applied to the updated member-based denominators.

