4.1. DENOMINATOR ESTIMATION

4.1.1. Site - specific approaches

The 2000 US Census non-institutionalized non-military resident population from which cases are present in the index year will be used as denominator. A “resident” is defined as a person with a permanent address within the defined geographic area at any time in the index year, who is not noted to be living elsewhere and only temporarily residing at the eligible address.

Military personnel and dependents are counted in the denominator for the county in which they currently reside. Military and dependents that have access to civilian medical facilities will be captured in the numerator. Those that use military facilities will be excluded. Firm estimates of the size of this bias are not available, though it appears they will be small. Starting with year 2002 Census data on socio-economic characteristics of population as well as counts of civilian and non-civilian individuals will be available. We will then be able to subtract military personnel from our denominators. There are 5 Colorado Springs Military Bases in Colorado: Fort Carson, Peterson Air Force Base, Schriber Air Force Base, the U.S. Air Force Academy, and NORAD, and one in Denver: Buckley Air Force Base.

Persons of Native American origin residing on eligible Native American reservations and counted in the census as on-reservation members are considered residents of the reservation, even if they live off-reservation for any period of time during the eligible time period. Children born on reservation during the index year will also be considered residents of the reservation.

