4.1.2. Denominators for prevalence

Prevalence of diabetes in youth aged 0-19 will be estimated for the year 2001 in the following geographic areas:

Urban-suburban counties, including the Denver-Boulder metropolitan statistical area, (Denver, Adams, Arapahoe, Douglas, Jefferson, and Boulder).

Rural Colorado counties, including the San Luis Valley (Conejos, Costilla, Alamosa, Sauguache, Mineral, Rio Grande) in south-central Colorado, and Mesa county in western Colorado. Selection of these counties was based on several reasons: a) they expressed interest in participating in the registry; b) a network of collaborators, health care providers, hospitals, etc, has already been developed through several previous studies in the San Luis Valley region; and c) their participation will help investigators learn about the ascertainment process in these areas, patterns of access to different sources of cases, patient referral patterns, and issues of confidentiality in different populations and provider groups.

Native American tribes on reservations in Arizona and New Mexico that have expressed interest to participate:

- a) Navajo Nation in Arizona and New Mexico
- b) Gila River Pima Indian Reservation in Arizona
- c) Apache Indian Reservations White Mountain (Fort Apache) and San Carlos in Arizona

These reservations were approached based on their size and on preliminary expression of interest.

The following table shows estimates of prevalence denominator by ethnicity, based on the 2000 US census

Age	NHW	African American	Hispanic	Asian	Pacific Islander	Native American	Total
0-19	564,465	42,251	105,217	14,848	3,712	132,265	862,758

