4.1. DENOMINATOR DETERMINATION

Prevalence of diabetes in youth less than 20 years of age was estimated for the year 2001 in the 8-county primary service area for CCCHMC. July 2001 age and gender specific projections derived from Census 2000 data for these 8 counties were used to determine the prevalence denominator. Since these 8 counties do not encompass any military installations, it was not necessary to adjust projections to compensate for military personnel in the denominator. Race data for the following racial/ethnic groups was based on the race-bridging modeling approach developed by the National Center for Health Statistics: Non-Hispanic White, African-American, Hispanic, Asian/Pacific Islander, and Native American/Alaska Native. In addition, zip code level geocoding was used to assign race to prevalent cases for whom race data was unknown (6).

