4.1. DENOMINATOR ESTIMATION

4.1.1. Site specific approaches

The 2000 US Census non-institutionalized non-military (NI-NM) resident population from which cases are present in the index year will be used as the primary denominator in sites using geographic-based denominators such as South Carolina. Use of this denominator will most closely align the population at risk for all sites.

Special Populations

College students: Such individuals are counted in the Census in their residence location as of April 1 2000, usually the college/town where they attend school. They will be included in the NI-NM denominators. There are three large research universities (University of South Carolina, Clemson University, and the Medical University of Charleston) and nine teaching colleges and universities within the South Carolina geographic area of interest. South Carolina also has 22 independent and private colleges and universities. Contact with the school(s) health services will be made to determine the estimated number of known cases, and the school's willingness to participate.

Military personnel: Military personnel are counted in the Census for the county in which they currently reside/are based. Initial total population estimates include them, however, as the Census results are further refined, the military members are identified separately. Final denominator estimates will exclude military service members, though they will be included in less refined estimates. There are three large military bases in South Carolina: Fort Jackson Army Base, Shaw Air Force Base, and the US Marine Corps Recruiting Depot - Parris Island. Fort Jackson, located in Richland County, is the largest basic training facility for the army, graduating approximately 40,000 soldiers each year. Shaw Air Force Base,

located in Sumter County, supports approximately 6,500 military and civilian workers and 6,000 family members.

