4.1.2. Denominator for prevalence

Prevalence of diabetes in youth aged 0-19 will be estimated for the year 2001 in each of the geographic areas and populations included in the SEARCH registry project.

In most geographic areas, projections beyond 2000 will not be available for some time. Thus, for the initial prevalence estimate, year 2000 denominator data will be used. Once projections for the year 2001 are available, and population subsets (non-institutional, non-military) are made by the South Carolina Health and Demographics Section, Office of Research and Statistics, State Budget and Control Board, prevalence estimates will be updated.

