4.2.3. Denominators for prevalence

For the initial prevalence estimate, the 2000 US Census will be used for the 5-county Puget Sound Region. Once projections based on the 2000 US Census are updated by the

WA State OFM, prevalence estimates will be updated. The estimated populations residing in the Puget Sound Region is summarized in Table 1.

Table 1. Estimated prevalence denominators by age group and ethnicity*

Age Group	Caucasian	African-American	Hispanic	Asian/PI	Native American	Total
0-4	181,272	15,990	12,775	19,884	3,811	233,732
5-9	202,115	16,456	13,592	23,143	3,972	259,278
10-14	200,586	15,295	12,933	22,884	4,119	255,817
15-19	179,879	14,042	11,546	24,550	4,076	234,093

*Based on 2000 census estimates [WA State Office of Financial Management]

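### Final 2001 prevalence denominators have no common reference date: the April 2000 Census in the core rule and at Colorado, July 2001 at Cincinnati, and December 31, 2001 at Southern California

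*Protocol*

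**What the plan says.** **Core rule (Section 4.2).** For Cincinnati, Colorado, Seattle and South Carolina: "For the prevalence component of the study, 2000 US Census data will be used". The paragraph on age, gender and race/ethnicity for prevalence repeats it: "Year 2000 Census data will be used to calculate age, gender, and race/ethnicity specific denominators". The two membership centers are to count members on July 1 of the given year.

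**Census date.** Core Section 4.2 gives April 1 when it discusses college students. The South Carolina section (4.1.1) adds the year: "Such individuals are counted in the Census in their residence location as of April 1 2000".

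**Site sections.**
- Colorado 4.1.1: "The 2000 US Census non-institutionalized non-military resident population from which cases are present in the index year will be used as denominator". Section 4.1.2 then gives the total of 862,758: "The following table shows estimates of prevalence denominator by ethnicity, based on the 2000 US census". Colorado plans to subtract military personnel later, but states no move to a 2001 population for prevalence.
- Cincinnati 4.1: "July 2001 age and gender specific projections derived from Census 2000 data for these 8 counties were used to determine the prevalence denominator". Section 4.1.2 gives the July 1, 2001 total as 549,356.
- South Carolina 4.1.2: year 2000 data for the initial estimate, with an update to follow: "Once projections for the year 2001 are available".
- Puget Sound 4.2.3: "For the initial prevalence estimate, the 2000 US Census will be used for the 5-county Puget Sound Region". Estimates are updated when the state issues projections; no reference date is given for the update.
- Southern California 4.1: members on 12/31/2001.
- Hawaii 4.1.2: plan members living on Oahu during 2001, with no count date.

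**Numerator (core 4.2.1.1).** Cases prevalent in 2001 who were resident at any time in that year, or plan members in that year.

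**The concern.** Core Section 4.2 says that cases and denominator must come from the same population. Applied literally, its own rule divides 2001 cases by a population counted 15 months before mid-2001. Of the four centers it names, only Colorado follows the rule through to the final estimate, so a reader cannot tell which denominator is final.

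Primary aim (a) rests on these rates. Section 8.1.1 reports them by site and combines them into national estimates. Cincinnati 4.3.1.1 also compares rates between sites and looks for explanations of differences. A difference in reference date is an avoidable source of such differences. It does not shrink as cases accumulate, and the confidence intervals in Section 8.2 do not reflect it.

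**Working it through.** **1. The plan's own precision (Section 8.2, Table 6-1).** Rate = 6,378 / 3,518,342 = 1.813 per 1,000. SE = √(p(1−p)/D) = 0.0227 per 1,000. Half-width = 1.96 × 0.0227 / 1.813 = 2.45%, against 2.5% stated, so it reproduces. The relative SE is 1/√6,378 = 1.25%.

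**2. Denominator shares (Appendix V, Table V-9).**
- Colorado: 455,993 + 406,765 = 862,758
- Seattle: 493,010 + 489,910 = 982,920
- South Carolina: 85,707 + 95,817 = 181,524

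With Cincinnati (550,430), Hawaii (240,260) and Southern California (700,450), these sum to 3,518,342, the total in Table 6-1.
- Colorado alone: 862,758 / 3,518,342 = 24.5%
- Colorado, Seattle and South Carolina: 2,027,202 / 3,518,342 = 57.6%

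Table 3-1 gives Colorado 808,503 of 3,461,801, which is 23.4%. Using it would barely change the results below.

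**3. The only pair of figures in the protocol.** Cincinnati has 550,430 in the planning tables and 549,356 for July 1, 2001: 549,356 / 550,430 − 1 = −0.2%. With 1,036 expected cases, the rate moves from 1.882 to 1.886 per 1,000. The pair is imperfect. Table 3-1 labels 550,430 a 2001 estimate, while the footnote to Table V-9 attributes such figures to the 2000 Census. Table V-9 also carries zeros for four racial/ethnic groups that the July 2001 table includes.

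**4. Effect of the date elsewhere.** From April 1, 2000 to July 1, 2001 is 1.25 years. At yearly growth g, a center left on 2000 data overstates prevalence by (1+g)^1.25 − 1. The crude pooled rate moves by that amount times the share of the denominator on 2000 data. The growth rates are assumptions.

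| Assumed g per year | Center on 2000 data | Pooled, Colorado only (× 0.245) | Pooled, Colorado + Seattle + South Carolina (× 0.576) |
|---|---|---|---|
| −1% | −1.2% | −0.3% | −0.7% |
| 0 | 0 | 0 | 0 |
| 1% | 1.3% | 0.3% | 0.7% |
| 2% | 2.5% | 0.6% | 1.4% |
| 2.5% | 3.1% | 0.8% | 1.8% |

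The Colorado-only column matches the site sections, under which Seattle and South Carolina update. The last column applies only if the core sentence were followed at all three centers.

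**5. Scale.** In the 1% to 2.5% range, the Colorado-only shift is 0.31/1.25 to 0.77/1.25, or about 0.25 to 0.6 standard errors of the pooled rate. The three-center shift is about 0.6 to 1.4. Colorado's own half-width is 1.96/√1,430 = 5.2%. Its growth would have to be about 4.1% per year for the date effect to equal that.

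**The case against.** - **The bias is assumed.** This stands. No growth rate is given, and the one in-document comparison is small and slightly negative. Only the direction under growth can be asserted.
- **South Carolina and Seattle move off 2000 data.** This stands. A provisional figure followed by an update is not a rival definition, so the Colorado-only column is the relevant one.
- **The alignment principle concerns inclusion criteria, not count dates.** Partly right. The core text applies it through eligibility criteria, and cases may be resident at any time in 2001, so no single-day count matches exactly. A count within 2001 is still closer than one from April 2000, and the site sections still disagree with the core rule.
- **The crude shares are not the final weights.** This stands. National estimates are adjusted for age, sex and race/ethnicity (8.1.1), so the pooled figures only indicate size.
- **There was a practical reason for starting with 2000 data.** South Carolina 4.1.2 says that later projections would take time. That justifies a provisional basis, not an unstated final one.

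A reader might infer that center rates cannot be compared, or that prevalence is overstated in fact. The documents support neither. The plausible shifts are a few percent, below the centers' own sampling half-widths (4.7% at Seattle to 10.3% at South Carolina among the four geographic centers) unless growth reaches about 4% per year or more. Overstatement depends on growth that the protocol does not report.

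**Conclusion.** The inconsistency is in the text and needs no outside figure: the final 2001 prevalence denominators do not share a reference date, and the core rule disagrees with site sections that it governs. The numerical consequence is conditional and modest. At an assumed 1% to 2.5% yearly growth, Colorado's prevalence would be overstated by about 1.3% to 3.1% and the crude pooled rate by 0.3% to 0.8%. The pooled range of 0.7% to 1.8% would need the core rule to override the updates planned at Seattle and South Carolina. The calculation treats the other centers' denominators as correct for 2001 and uses crude weights. The point deserves correction because it affects a primary-aim denominator and is inexpensive to settle.

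**What to change.** In core Section 4.2, and in its paragraph on age, gender and race/ethnicity for prevalence, state that final prevalence denominators at all centers refer to July 1, 2001. The four geographic centers would use population estimates based on the 2000 Census, and the two plan-based centers would use membership counts. Keep 2000 Census figures for provisional estimates only.

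Then align the site sections: Colorado 4.1.1 and 4.1.2, South Carolina 4.1.2, Puget Sound 4.2.3 (name the date of the update), Southern California 4.1 and Hawaii 4.1.2. Cincinnati already conforms. Southern California 4.2.1 also ties case eligibility to membership on 12/31/2001. Its case date and its denominator date should therefore move together, since moving the denominator alone would break the alignment that the site now has.

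**Cost.** New wording and a re-run of denominators. Cincinnati has done this, South Carolina and Seattle plan an update, and Colorado 4.1.3 already uses projections for incidence. Those Colorado projections start in 2002, however, so 2001 estimates for its selected counties and reservations would have to be obtained. Projections bring some error, especially by race/ethnicity and for the reservation populations. Where 2000 race/ethnicity proportions are applied to 2001 totals, as the core text allows for incidence, growth that differs by race stays uncorrected. The change should not be presented as removing it.
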